4.0 Research Plan and Methods

This is a **single-center pragmatic phase II open-label randomized controlled trial** to compare two standardized bundles of usual care for postoperative pain management. The single difference in intervention is an additional QL block on POD4 in patients undergoing sarcoma surgery with potentially curative intent. The **primary endpoint is the initial discharge prescription OME**. Patients will be randomized with 1:1 ratio to receive either QL in OR + non-opioid bundle +/- low-dose IV-PCA (control arm) or QL in OR and QL on POD4 AM + non-opioid bundle +/- low-dose IV-PCA (experimental arm). The **randomization will occur on postoperative day 3** so that usual care will be performed intraoperatively and for the first 3 days after surgery. On POD3, at the time of randomization, patients will be stratified based on preoperative use of long-term opioids (e.g. extended or continuous release) (yes vs. no) and preoperative average daily OME use ($>7.5\text{mg}$ vs. $\leq7.5\text{mg}$ OME, which allows 1 tramadol, 1 oxycodone, or 1 hydrocodone per day in the lower stratum) in the 7 days before surgery. Patients will further be stratified by whether they undergo nephrectomy (yes vs. no) as part of their operative procedure, or if they have a previous surgical history of nephrectomy, as this would impact their eligibility for some of our frequently used adjunct pain medications (e.g. Celebrex, Toradol). There will be no standardization of postoperative dietary advancement, fluid management, or postoperative care, other than standardization of the IV and oral non-opioid bundle and initial IV-PCA settings in the recovery room on POD0.

Method of Group Assignment and Randomization

- **Stratified Randomization:** REDCap will be used for 1:1 allocation and stratification for preoperative long-term (≥ 3 months) opioid use (yes vs. no), preoperative average daily OME use ($>7.5\text{mg}$ vs. $\leq7.5\text{mg}$ OME), and nephrectomy status (yes vs. no), as detailed above.
- **Implementation:** Acute pain team, surgeons, advanced practice providers, fellows, and nurses will perform interventions and assessments per usual care.
- **Blinding:** This is an open-label study since the intervention arm will receive a 2nd QL block which cannot be blinded from the patient or treating physician. The allocation will be unmasked immediately upon randomization on POD3 morning after clinician rounds.

Intervention Strategy:

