On postoperative day 4 [at least 96hrs from initial QL on postoperative day “0”, which is the day of surgery, per FDA guidelines], patients will undergo a 2nd QL procedure in the regular

hospital room by the Acute Pain Service attending anesthesiologist using ultrasound guidance, which is usual routine method. The intent will be to do the 2nd QL. Patients or providers may choose to forego the option if patients are already opioid-free or nearly opioid-free or for any other reasons provided by the patient.

This will be a **4-point Type I QL + subcostal block**, which allows an anterior approach to the targeted fascial layers. Using sterile technique, the attending anesthesiologist will guide the needle through the appropriate skin, subcutaneous, and muscle layers to find the right fascial plane **using ultrasound localization**. The risk of complications is virtually nil, because most hospital subcutaneous and intramuscular shots which are done blindly or by “landmark,” the QL block will be done by exact ultrasound guidance. **This block will only be done by Acute Pain Service certified faculty**. We are not studying this block’s mechanism or the drug’s mechanism – both of which are well documented in thousands of patients. **This pragmatic RCT focuses on the novel timing of using this regional block to measure its effectiveness in accelerating the opioid weaning process.**

Patients will not be randomized if anticipated to be discharged by 7am on POD4, or if they are already opioid-free on POD3 at time of randomization. The clinical team will be able to anticipate any early discharges (defined as discharge before POD4) and therefore exclude those patients from randomization.

(The **usual measures of non-opioid bundle** [including acetaminophen, NSAIDs, muscle relaxers] and conversion from IV pain meds to oral pains will be done to reduce total opioid exposure and use. Clinicians may choose to add additional non-opioids if clinically indicated. Non-opioids will be standardized for dosing, timing, and route, and will be given unless contraindicated (e.g. holding NSAIDs if nephrectomy performed for the sarcoma resection).

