 - **Dosage instructions in Figure 3 below.** The Operating Room pharmacy has calculated the appropriate max dose of long-acting and short-acting bupivacaine, which can be safely mixed. There are laminated placards in every operating room as protective measures to prevent dosage miscalculations, and most nurses know the mixture. The Acute Pain Service attendings know as well since they have performed thousands of these injections in the past few years at our institution.
 - **Liposomal bupivacaine has become our standard of care for open surgery.** We use this in the majority of our open abdominal cancer surgery patients, while an ever-decreasing minority still get epidurals. There is extensive experience using liposomal bupivacaine for regional blocks. This RCT does not focus on the use of the block per se (since it is routine or usual care), but rather the timing of it.

Comparison Strategy:

The comparison arm patients will have usual care with just the single QL using ultrasound guidance placed in the OR. When the liposomal bupivacaine wears off, **there will be no second QL block.** The **usual measures of non-opioid bundle** [including acetaminophen, NSAIDs, muscle relaxers] and conversion from IV pain meds to oral pains will be done to reduce total opioid exposure and use.

Decision on Discharge Opioid Prescription

To avoid bias in one arm or the other, all discharge prescriptions will be standardized. Both arms will get standard non-narcotic bundles of acetaminophen 650mg q6hrs, celecoxib 100mg q12hrs, and methocarbamol 250-500mg q8hrs. Slight dose variations can be allowed here based on pharmacy availability (e.g. recent national shortage of methocarbamol 500mg pills). Patients who undergo nephrectomy will not receive celecoxib due to risk of renal insufficiency. To standardize the opioids, we will use a multiplier of 5x the last-24hrs OME count. This 24-hr count can be easily found in the electronic health record and will be taken from the time of final discharge prescription writing. If this is POD4, it will be calculated after the 2nd block, if one is administered. We chose 5x because the CDC recommends 7 days max prescription and less than 200mg OME. All patients have

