5.0 Statistics and Justification of Sample Size

For the primary analysis, we will perform two-sample t-test to compare the mean doses of **discharge prescription OME** between the two groups. In addition, multiple linear regression analysis will be carried out to assess the difference between the two arms after adjusting for the stratification factors and other patient characteristics at baseline. Similar analyses will be performed for other continuous secondary outcomes such as total length of stay, 30-day total OME, initial discharge pain prescription dosage/size, number of postoperative days until zero opioid use, etc. Logistic regression analyses will be performed for binary secondary outcomes, such as discharge prescription OME = zero, discharge Rx dosage/size total OME <200mg (yes vs. no), opioids use at POD 30 (Y/N), etc. For repeated measures, linear mixed model will be used for continuous outcomes such as daily inpatient pain scores and GEE model will be fit for binary outcomes such as opioid use at various time points. Other statistical analyses may be performed as appropriate.

Based on historical data as of August 2019, the **mean discharge OME** for the comparison arm was about **200 mg (standard deviation 200mg)** and we anticipate that with a **second, repeat QL block**, the discharge OME for the intervention arm will reduce to **75 mg**.

Under this assumption and assuming a common SD of 200, the study will require 84 patients (42 in each arm) in order to have 81% power to detect the difference in discharge OME with a two-sided 5% significance level. East 6 was used for the sample size calculation. Assuming a liberal 20% dropout rate, a total of 106 patients will be enrolled from our single institution. Based on our historical operation volume of 120 patients per year, we anticipate the ability to complete enrollment within 1 year of opening the protocol. One interim analysis will be performed when half of the patients (N=42) have been randomized. The trial will be stopped due to futility if the p-value is >0.732.

- Power and significance: 81% power ($\beta=0.19$) and $\alpha=0.05$ (two-sided)
- Baseline estimate of mean comparison/control arm: 200mg OME
- Estimate of mean experimental arm: 75mg OME
- Sample size per arm: 42 pts
- Assume 20% dropout: 53 per arm
 - [1 year to complete enrollment]

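### The primary t-test leaves out the 24-hour opioid count before POD3 randomisation, a baseline for the endpoint that could add precision at almost no cost

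*Combined protocol and SAP*

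**What the plan says.** Section 5.0 (Statistics and Justification of Sample Size) makes an unadjusted comparison primary: "For the primary analysis, we will perform two-sample t-test to compare the mean doses of" discharge OME. The plan then adds that "multiple linear regression analysis will be carried out to assess the difference between the two arms after adjusting for the stratification factors and other patient" factors; those baseline factors are not listed. The sample size rests on the t-test alone: control mean 200 mg, experimental mean 75 mg, common SD 200 mg, two-sided 5%, 42 per arm, 81% power.

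Section 4.0 supplies the rest:

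- **Endpoint.** The discharge prescription is fixed at 5 times the OME of the last 24 inpatient hours. Of that count the protocol says "This 24-hr count can be easily found in the electronic health record".
- **Timing.** Patients are randomised on POD3, so that "usual care will be performed intraoperatively and for the first 3 days after surgery". The second block follows on POD4.
- **POD3 check.** Patients are not randomised if discharge is expected by early morning on POD4, "or if they are already opioid-free on POD3 at time of randomization".
- **Strata.** Long-term preoperative opioid use, average daily OME in the 7 days before surgery (cut at 7.5 mg), and nephrectomy.

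**The concern.** The endpoint is a scaled 24-hour opioid count. Because randomisation waits until POD3, each patient has a value of that same kind of count from before the arms diverge, and the primary analysis makes no use of it. The strata do not stand in for it: they describe opioid use before surgery and kidney status, not how much opioid the patient needs after this operation with the first block in place.

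Precision is at stake. The assumed SD (200 mg) equals the control mean and there are only 42 patients per arm, so the arm difference will be estimated with a wide interval. Any part of the between-patient variation that POD3 use predicts can be removed by adjustment. Left in, it widens the interval, and a chance imbalance in POD3 use moves the estimate in proportion to how well that use predicts discharge OME.

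**Working it through.** **Inputs from Section 5.0:** "Baseline estimate of mean comparison/control arm: 200mg OME"; "Estimate of mean experimental arm: 75mg OME"; so the difference is 200 − 75 = 125 mg. SD 200 mg in both arms, n = 42 per arm, two-sided α = 0.05.

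**Step 1: reproduce the plan.** Standard error = 200 × √(2/42) = 200 × 0.2182 = 43.6 mg. Noncentrality = 125 / 43.6 = 2.86. Power from the noncentral t with 82 df is 80.8% (81.7% by the normal approximation), matching the stated 81%. The 95% CI half-width is 1.989 × 43.6 = 86.8, about 87 mg. With 20% dropout, 42 / 0.8 = 52.5, so 53 per arm and 106 in total, as stated.

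**Step 2: add the covariate.** Let r be the within-arm correlation between OME in the 24 hours before randomisation and discharge OME. The documents give no value, so r is an assumption, shown over a range.

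- Residual SD = 200 × √(1 − r²).
- Power: noncentral t with 81 df (one df spent on the covariate) and noncentrality 125 / (residual SD × 0.2182).
- Half-width = 1.990 × residual SD × 0.2182.

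| Assumed r | Residual SD (mg) | Power | 95% CI half-width (mg) |
|---|---|---|---|
| Unadjusted | 200 | 80.8% | 87 |
| 0.1 | 199 | 81.2% | 86 |
| 0.2 | 196 | 82.3% | 85 |
| 0.3 | 191 | 84.3% | 83 |
| 0.5 | 173 | 90.5% | 75 |
| 0.7 | 143 | 97.7% | 62 |

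At r = 0.5 the gain equals having 42 / (1 − 0.25) = 56 patients per arm. Spending three more df on the three two-level strata changes these powers by less than 0.1 percentage point. No credit is taken for any variance the strata themselves explain.

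**Step 3: chance imbalance.** A one-standard-error imbalance in the POD3 count is √(2/42) = 0.22 SD. It moves the unadjusted arm difference by r × 200 × 0.2182: about 4 mg at r = 0.1 and about 22 mg at r = 0.5.

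**Step 4: is the adjustment legitimate?** The count is postoperative, but it precedes randomisation and the second block, so the allocated arm cannot have affected it. It is a proper baseline for the randomised comparison.

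**The case against.** The strongest reply is that nothing here is broken: the t-test is valid, the sample size is right, and a regression with baseline adjustment is already planned. Its parts stand to different degrees.

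- **The planned regression may already cover it.** Randomisation is on POD3, so a POD3 value could count among the unlisted baseline characteristics. A reader might infer that the plan rules the count out; the text supports only that it is not named. But that regression is supplementary. Adding the covariate there alone would leave the primary test at 80.8% power and 87 mg.
- **Bias.** A reader might infer that a POD3 imbalance could make the trial falsely positive. Randomisation and the 5% error rate already allow for chance imbalance, so the planned test is neither biased nor invalid.
- **The correlation may be low.** This stands. Excluding patients who are opioid-free on POD3 restricts the range, and the interval to discharge varies. The first block is described as acting for 72 hours, so the POD3 window falls largely within its action and the discharge window after it. Part of the POD3 count may come from IV-PCA, which is weaned as solid food starts. At r of 0.1 or 0.2 almost nothing is gained.
- **Availability.** The remark about the health record concerns the count at discharge, and the POD3 check is only opioid-free or not. That a POD3 total can be extracted is a close inference, not a documented fact.
- **Binary outcomes.** The precision argument does not carry over to the logistic models. Section 2.0 reports 5% opioid-free discharge across five index operations; at that rate 84 patients would give 0.05 × 84 ≈ 4 events, too few to support another covariate.

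**Conclusion.** The point holds as a cheap improvement. The primary analysis is unadjusted, the 24-hour OME before POD3 randomisation is a valid baseline for an endpoint built from a 24-hour OME, and no part of the plan names it. The plan's own power is correct.

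The gain is of unknown size. Over assumed r from 0.1 to 0.7, power goes from 81.2% to 97.7% and the half-width from 86 to 62 mg, against 80.8% and 87 mg. These figures rest on the plan's 125 mg difference and 200 mg SD, 42 analysed per arm, a linear relation, and normal-theory calculation. An SD of 200 mg against means of 200 and 75 mg, for a quantity that cannot be negative, implies skew, so they are approximate. The documents do not support claiming any particular r.

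**What to change.** In Section 5.0:

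1. Make the primary analysis a linear model (ANCOVA) of discharge OME on arm, adjusted for OME in the 24 hours before randomisation and for the stratification factors. Enter the POD3 count as a continuous variable, taken from the electronic health record with the same OME conversion as the endpoint.
2. Specify robust standard errors, because of the expected skew.
3. Use the same model for the primary-endpoint p-value at the interim futility look.
4. Keep the two-sample t-test as a sensitivity analysis.
5. The covariate may also be used for 30-day total OME. Do not add it to the logistic models for binary outcomes.

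The cost is a few sentences in Section 5.0, one derived field recorded when the POD3 opioid-free check is made, and one degree of freedom. No patients, visits or procedures are added. Before finalising, confirm that the POD3 24-hour total can be extracted for every randomised patient. The gain may turn out small.

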- Number of postoperative days until zero opioid use
- Opioid use at 30 days, 3 months, and 12 months (Y/N, OME)
- MDASI-GI at 30 days, 3 months, and 12 months
- 3-mo and 1-yr follow-up – patients free of opioid use (Y/N)

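### Days until zero opioid use is a time-to-event outcome, but section 5.0 gives it a t-test and linear regression with no rule for patients who have not reached zero

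*Combined protocol and SAP*

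**What the plan says.** Section 1.0 lists "Number of postoperative days until zero opioid use" as a secondary discharge measure. Section 5.0 sets the primary analysis as a two-sample t-test plus multiple linear regression and then states: "Similar analyses will be performed for other continuous secondary outcomes such as total length of stay". The list that follows includes "initial discharge pain prescription dosage/size, number of postoperative days until zero opioid use, etc". The t-test and regression therefore reach this outcome by reference, but the reading is not in doubt.

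The documents do not define zero (first opioid-free day or sustained freedom), set a last day of observation, or name a censoring rule or a time-to-event method. The only further provision is "Other statistical analyses may be performed as appropriate", which supplies no rule. Persistent use is also covered by separate yes/no outcomes at 30 days, 3 months and 12 months, for which a "GEE model will be fit for binary outcomes such as opioid use at various time points".

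**The concern.** The number of days to an event is defined only for patients who have the event. Three features of the plan make patients without it foreseeable:

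- Freedom from opioids at 3 months and at 1 year is itself a yes/no outcome (section 1.0).
- Long-term opioid users are eligible and form a randomisation stratum (sections 3.0 and 4.0).
- The hypothesis expects the arms to differ in the proportion who become free of opioids (section 2.0).

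A t-test needs a number for every patient it includes. Dropping those without one selects on a post-randomisation outcome that the treatment is expected to change, and removes the patients in whom an effect on persistent use would show. Coding them to a day puts an arbitrary constant into the analysis. The trial is open-label, so a rule left unstated could be settled after outcomes are known by arm.

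**Working it through.** **The plan's own figures.** The documents give no stopping rate, stopping time or power for this outcome. The 42 per arm comes from the primary endpoint and reproduces: noncentrality (125/200) × √(42/2) = 2.86 on 82 degrees of freedom gives 80.8% power, against the stated 81%.

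**Inputs.** From section 5.0: 42 per arm and a two-sided 5% level. Assumed: share not reaching zero *p*, mean day among stoppers *m*, day *c* given to non-stoppers. Differences are control minus intervention.

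**Formulas.** Arm mean if coded = *p·c* + (1−*p*)·*m*; if dropped, *m*. Arm variance if coded = (1−*p*)·*s*² + *p*(1−*p*)(*c*−*m*)², with *s* the SD among stoppers. SE = √(sum of the two variances / 42).

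**Case 1: non-stopping differs, stoppers average 20 days in both arms.**

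- 20% vs 5%, dropped: 20 − 20 = 0.
- 20% vs 5%, day 90: (0.20×90 + 0.80×20) − (0.05×90 + 0.95×20) = 34.0 − 23.5 = 10.5 days. SE 4.9 to 5.8 for *s* from 0 to 15.
- 20% vs 5%, day 365: 89.0 − 37.25 = 51.75 days, SE about 24.
- 10% vs 5%: 0 dropped; 27.0 − 23.5 = 3.5 at day 90 (SE 4.0 to 5.1); 54.5 − 37.25 = 17.25 at day 365 (SE about 20). Both coded differences are under one SE.

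**Case 2: equal non-stopping of 10%, medians 14 vs 8 days.** With exponential times the means are 14/ln 2 = 20.20 and 8/ln 2 = 11.54. Dropped, the difference is 8.66. Coded, *c* cancels and it is 0.9 × 8.66 = 7.79 for any code. The variance does not cancel:

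- Dropped (about 37.8 per arm): SE = √((20.20² + 11.54²)/37.8) = 3.8.
- Day 90: arm variances 0.9×20.20² + 0.09×69.80² = 806 and 0.9×11.54² + 0.09×78.46² = 674; SE = √(1480/42) = 5.9.
- Day 365: the same formula gives 11,067 and 11,364; SE = √(22,431/42) = 23.1.

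**Case 3: both effects, 10% vs 5%, medians 14 vs 8.** Dropped 8.66 days; day 90, 27.18 − 15.46 = 11.72; day 365, 54.68 − 29.21 = 25.47.

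**Share of simulated trials with p < 0.05** (20,000 trials, 42 per arm, exponential times from randomisation, pooled t-test):

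| Assumed non-stopping; medians | Dropped | Day 90 | Day 365 |
|---|---|---|---|
| 20% vs 5%; 14 vs 14 | 5% | 37% | 56% |
| 10% vs 5%; 14 vs 14 | 5% | 9% | 12% |
| 10% each; 14 vs 8 | 64% | 26% | 6% |
| 10% vs 5%; 14 vs 8 | 66% | 58% | 25–26% |

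In the third row, lognormal times (log SD 0.7 to 1.0) give 86% to 49% dropped and 6% to 7% at day 365, so the pattern does not come from the exponential shape.

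**The case against.** The strongest reply is that the t-test is not itself the fault. With complete follow-up, a t-test on days truncated at day 90 and a Kaplan-Meier restricted mean to day 90 nearly coincide (rejection 26% vs 27% in case 2, 38% vs 40% in case 1 at 20% vs 5%). What is missing is a rule. That largely stands. It does not rescue the plan as written, which has no rule, and truncation alone does not handle patients lost before the horizon.

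The large contrasts also come from one-sided scenarios. When faster weaning and less persistence occur together, as the hypothesis expects, dropping and day-90 coding are close; only day 365 departs sharply, and the plan nowhere proposes that code. This stands.

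Several stronger readings are tempting and are not supported:

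- A reader might take "Assuming a liberal 20% dropout rate" as evidence of unobserved stopping days. Section 5.0 places the interim at 42 randomised and calls that half, which implies 84 randomised out of 106 enrolled. The dropout therefore probably precedes randomisation on POD3.
- A reader might cite the rule against randomising patients already opioid-free on POD3. That removes very early stoppers; it does not create patients who never stop.
- A reader might infer that the code always moves the mean difference. With equal non-stopping it does not (case 2).
- A reader might infer that persistent users vanish from the trial's results. The logistic and GEE analyses of opioid use still count them.

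**Conclusion.** The point holds in limited form. Section 5.0 assigns a method for fully observed continuous data to a time-to-event outcome, in a population where some patients will foreseeably lack the event, and gives no rule for them. Where non-stopping differs by arm, the rule sets the estimated difference; where it is equal, the rule changes mainly the variance and power. The size rests wholly on assumed non-stopping rates and stopping times, so the figures show sensitivity to the rule and do not predict the trial's result.

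A reader might extend this to the trial's main conclusion. The documents do not support that: the primary endpoint, the sample size and the type I error of the primary test are untouched. The change should be made, but it concerns one unpowered secondary outcome.

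**What to change.** In section 5.0, take this outcome off the t-test and linear regression list and add one paragraph that:

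- defines the event once, for example the first day of sustained zero use;
- analyses it as time to event in postoperative days, censoring patients not at zero at last contact and counting deaths before zero as not reaching zero up to the horizon;
- compares the arms by Kaplan-Meier curves and the difference in restricted mean days to one horizon fixed before data are seen (for example day 90), adjusted for the stratification factors.

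If the stopping day is known only from the 30-day, 3-month and 12-month contacts, use an interval-censored analysis and state that it leans more on model assumptions, or rely on the binary opioid-use outcomes. That fallback has not been tested here. Whether the exact day is recorded cannot be told from the text, because the timeline figure is not shown. If it is recorded, no new data are needed.

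The cost is a result that depends on the horizon. On the assumptions above, day 90 rejects about 26% to 27% in case 2 and 38% to 40% in case 1 at 20% vs 5%; day 30 gives about 47% to 50% and 15% to 16%. An early horizon favours a faster wean and a later one favours less persistent use, so it must be fixed in advance. With complete follow-up the gain over a truncated t-test is only the fixed rule. With losses the gain is real: with an assumed 20% lost at random before day 90 in case 2, the restricted mean difference stayed at its true value of about 7.6 days, with a simulated type I error of 5.8%.
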